5.3.4 Electrocardiogram

The 12-lead ECGs will be recorded as scheduled in the Flow Chart. The investigator or a designee will evaluate whether the ECG is normal or abnormal and whether it is clinically relevant, if abnormal. ECGs may be repeated for quality reasons and the repeated recording used for analysis.

Additional ECGs may be recorded for safety reasons. Dated and signed printouts of ECG with findings should be documented in patient's medical record.

Clinically relevant abnormal findings will be reported either as baseline condition (if identified at the screening visit) or otherwise as adverse events and will be followed up and/or treated as medically appropriate.

5.3.5 Other safety parameters

5.3.5.1 Height and Body Mass Index (BMI)

Height and weight will be measured at the time points indicated in the Flow Chart.

Height should be measured using the same stadiometer for one patient.

SDS (Standard Deviation Score), e.g. z-score, values for height and BMI will be calculated by the sponsor for the statistical analysis using the WHO age-specific references.

5.3.5.2 Self-blood glucose monitoring

All patients will be provided with SBGM equipment (i.e. an electronic blood glucose monitoring device/meter that is also capable of measuring blood ketones) and supplies for use

at home during the study for self-measurement of blood glucose. Instructions on the proper use of the SBGM equipment will be provided by the site staff. The patient or his/her parent(s)/legal guardian will be asked to enter data from the device to a patient diary. The investigator or delegated site personnel should also print out the record list and include it in the patient medical records. To avoid additional finger pricks for blood glucose measurement, patients with a continuous glucose monitoring (CGM) device can use relevant readings from the device following the minimum testing requirements below. It is the PI discretion to report clinically relevant readings as adverse events. It is also the PI discretion regarding patient diary management entry as long as the minimum testing requirements below are met.

Only in case of linked adverse events, the single value from the glucometer will be recorded in the eCRF.

SBGM should be performed regularly and ideally its frequency should be individualised as per local clinical guidelines. Especially for patients on insulin, more frequent SBGM may be performed. Nevertheless, minimum requirements are defined by this clinical trial protocol and are as follows:

- Placebo run-in period

Daily SBGM in a fasted state is recommended.

- Randomised treatment period

SBGM at least 3 times per week in a fasted state is recommended.

- Follow-up period

At least one SBGM per week in a fasted state is recommended.

Throughout the trial, additional blood glucose measurements may be performed any time the patient is symptomatic, i.e. experiences signs/symptoms of hyper- or hypoglycaemia.

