5.3.5.6 Criteria for hypoglycaemic event

Every episode of plasma glucose equal to or below 70 mg/dl (3.9 mmol/l) should be documented in the eCRF with the respective time and date of occurrence. Any hypoglycaemia with glucose values < 54 mg/dl (< 3.0 mmol/l) as well as all symptomatic and severe hypoglycaemic event (requiring active assistance by another person to administer carbohydrate) should be documented with the respective time and date of occurrence as an AE "hypoglycaemic event".

For the analysis, all hypoglycaemias will be classified according to the following criteria:

- Documented symptomatic hypoglycaemia AE with glucose concentration \leq 70 mg/dL (< 3.9 mmol/L), as well as asymptomatic hypoglycaemia event \leq 70 mg/dL (< 3.9 mmol/L)
- Documented any hypoglycaemia AE with glucose concentration < 54 mg/dL (< 3.0 mmol/L)
- Severe hypoglycaemia AE: event requiring the assistance of another person to actively administer carbohydrates, glucagon or take other corrective actions. Plasma glucose concentrations may not be available during an event, but neurological recovery following the return of plasma glucose to normal is considered sufficient evidence that the event was induced by a low plasma glucose concentration [R17-0216].

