## **Hypoglycaemia**

The investigator will record for each AE whether it represents a hypoglycaemic AE and, if so, record additional information to assess the intensity of the hypoglycaemic AE. On the basis of this information the investigator-defined hypoglycaemic AE will be classified as:

- Documented symptomatic hypoglycaemia AE with plasma glucose concentration  $\leq 70$  mg/dL ( $< 3.9$  mmol/L), as well as asymptomatic hypoglycaemia AE with plasma glucose concentration  $\leq 70$  mg/dL ( $< 3.9$  mmol/L)
- Documented (any) symptomatic and asymptomatic hypoglycaemia AE with plasma glucose concentration  $< 54$  mg/dL ( $< 3.0$  mmol/L)
- Severe hypoglycaemia AE: event requiring the assistance of another person to actively administer carbohydrates, glucagon or take other corrective actions. (Plasma glucose concentrations may not be available during an event, but neurological recovery following the return of plasma glucose to normal is considered sufficient evidence that the event was induced by a low plasma glucose concentration.)

Reported hypoglycaemia (investigator-defined hypoglycaemia) adverse event is defined as hypoglycaemia adverse event reported in the eCRF AE page.

Any hypoglycaemia (protocol-defined hypoglycaemia) is defined as reported hypoglycaemia adverse event or asymptomatic hypoglycaemia non-AE that had plasma glucose between  $\geq 54$  mg/dL ( $\geq 3.0$  mmol/L) and  $\leq 70$  mg/dL ( $< 3.9$  mmol/L).

Any hypoglycaemia that occurs on the same day, but, with a different start time, will be handled as a separate hypoglycaemic event.

The number and percentage of patients with reported hypoglycaemia AE will be tabulated by treatment, SOC and preferred term.

The characteristics of the episodes will be presented separately for the reported hypoglycaemia AEs and any hypoglycaemia.

Similarly as for the analysis on patient level, a summary on the number of any hypoglycaemia, descriptive event rate, number of episodes by severity will be produced per patient-years. Only apply to TG1 and TG6.

A frequency table will be provided for number and percentage of patients with symptomatic hypoglycaemia adverse event with confirmed plasma glucose  $< 54$  mg/dL ( $< 3.0$  mmol/L) and/or severe hypoglycaemia AE by baseline age at randomisation in categories. See [Table 6.4:1](#) for the subgroup details.

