The treatment phase assignment of any hypoglycaemia (AE and non-AE) is exclusively based on the collected start date. These tables will be summarised up to the day before Week 26 by TG1 using TS, up to Week 52 by TG6 using TSactive and from the start of Week 14 to Week 52 by TG4 using TS (only patients re-randomised at Week 14) unless stated specifically.

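### Protocol 5.3.5.2 and 5.3.5.6 give conflicting rules for entering low glucose values in the eCRF, so capture for the SAP's 'any hypoglycaemia' tables may vary by site and device

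*Protocol*

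**What the plan says.** Protocol 5.3.5.2 (Self-blood glucose monitoring) restricts what leaves the home-testing log: "Only in case of linked adverse events, the single value from the glucometer will be recorded in the eCRF". The rest stays in the patient diary and in a device printout filed in the medical records. For children who use a CGM, the section adds "It is the PI discretion to report clinically relevant readings as adverse events" and "It is also the PI discretion regarding patient diary management entry as long as the minimum testing requirements below are met".

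Protocol 5.3.5.6 (Criteria for hypoglycaemic event) sets a wider rule: "Every episode of plasma glucose equal to or below 70 mg/dl (3.9 mmol/l) should be documented in the eCRF", with date and time and no AE condition. It then says that "Any hypoglycaemia with glucose values < 54 mg/dl (< 3.0 mmol/l) as well as all symptomatic and severe hypoglycaemic event" are to be documented as an AE. No investigator discretion is mentioned.

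SAP 7.8.1.5 (Hypoglycaemia) builds on the second rule: "Any hypoglycaemia (protocol-defined hypoglycaemia) is defined as reported hypoglycaemia adverse event or asymptomatic hypoglycaemia non-AE that had plasma glucose between" 54 and 70 mg/dL inclusive. It plans episode characteristics for this category separately from reported AEs, and event counts and rates per patient-year for TG1 and TG6. It also expects non-AE episodes to be in the database: "The treatment phase assignment of any hypoglycaemia (AE and non-AE) is exclusively based on the collected start date".

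The safety endpoint listed in Protocol 5.1.3.2 is narrower. It is the percentage of patients with *reported* hypoglycaemia, which the SAP takes from the eCRF AE page.

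**The concern.** A site cannot follow both protocol sections for an asymptomatic low reading that is not an AE. One section keeps the value out of the eCRF and the other wants the episode in it. Neither cross-refers to the other or says which prevails. For CGM users there is a second conflict, because one section makes AE reporting discretionary where the other requires it.

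The matter at stake is how completely hypoglycaemia is described in a paediatric trial. Protocol 2.3 relies on self-monitoring under 5.3.5.2 to watch for hypoglycaemia, and it notes that major events may increase when empagliflozin is added to insulin. Insulin background is allowed in the main study. If capture depends on which section a site reads and which device a child owns, the *any hypoglycaemia* figures will not mean the same thing across sites.

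**Working it through.** The plan states no figure for this point, so the check sets the three rules side by side. The 62 and 50 mg/dL readings are illustrations.

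| Reading | Protocol 5.3.5.2 | Protocol 5.3.5.6 | SAP *any hypoglycaemia* |
|---|---|---|---|
| Meter, asymptomatic, 62 mg/dL, no AE | value not entered | episode entered | counts, if episode and value are in the database |
| Meter, asymptomatic, 50 mg/dL | value entered, as it is linked to an AE | AE | counts as an AE |
| Meter, symptomatic, 70 mg/dL or below | value entered, as it is linked to an AE | AE | counts as an AE |
| CGM, asymptomatic, 62 mg/dL, no AE | diary entry discretionary; silent on the eCRF | episode entered | counts, if entered |
| CGM, 50 mg/dL, investigator sees no clinical relevance | AE report discretionary | AE | counts only if reported as an AE |
| Severe event | value entered if there is one | AE, with or without a value | counts as an AE |

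**Meter users.** The rules collide in one row only, the asymptomatic non-AE reading of 54 to 70 mg/dL. That row is exactly the SAP's non-AE limb for meter users.

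**CGM users.** The collision is over AE reporting. A 50 mg/dL reading that is not reported as an AE also falls outside the non-AE limb, which starts at 54 mg/dL. It would then appear in neither limb.

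**Effect on the event rate.** Let A be reported hypoglycaemia AEs, B the asymptomatic non-AE episodes of 54 to 70 mg/dL, T the patient-years and p the share of B that reaches the eCRF.

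- Intended rate: (A + B)/T
- Rate obtained: (A + pB)/T
- Shortfall: (1 − p)B/T

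With p = 1 (all sites follow 5.3.5.6) the shortfall is 0. With p = 0 (all sites follow 5.3.5.2 literally) the rate obtained is A/T, the same as for reported AEs alone, and the relative loss is B/(A + B). The documents give no value for A, B, p or the number of CGM users, so nothing narrower than this range can be stated. At patient level, only children whose sole episodes belong to B drop out. Unreported CGM events would lower A as well, and hence the reported-AE figures.

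**The case against.** The strongest reply is that the sponsor's intention is clear. Section 5.3.5.6 is the dedicated hypoglycaemia section and its eCRF rule is unconditional. The log for Global Amendment 1 shows that its threshold was revised deliberately to include 70 mg/dL. The SAP speaks of collected start dates for non-AE episodes. The eCRF and its completion guidance, which may settle the matter, are not among the documents. This stands, and it is why the finding is about variable capture. A reader might infer that the non-AE limb will be empty by construction; the documents do not show that.

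A second reply is that the sections cover different things: 5.3.5.2 governs transcription of routine log values, while 5.3.5.6 asks for an episode with date and time and does not expressly ask for the value. This narrows the conflict without removing it. Section 5.3.5.6 goes on to classify episodes by glucose concentration, and the SAP limb is bounded at 54 and 70 mg/dL. A band could be inferred for an episode without a value only if every value below 54 mg/dL had been reported as an AE, and CGM discretion weakens that assumption.

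Third, the discretion sentence can be read as covering clinically relevant readings in general, without waiving the specific rule below 54 mg/dL. That reading is fair, but the text does not state it.

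Fourth, the tables are descriptive, Protocol 7.3.6 plans no hypothesis tests on safety, and treatment is double-blind. So there is no evident reason for the loss to differ systematically between arms. This limits the consequence mainly to the completeness of the absolute figures.

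**Conclusion.** The textual conflict is certain and its numerical effect is unknown. At sites that follow 5.3.5.2 literally, the *any hypoglycaemia* tables and rates for TG1 and TG6 may be understated and approach the reported-AE results. The loss lies between none and all asymptomatic non-AE episodes of 54 to 70 mg/dL. This rests on the assumption that some sites would act on 5.3.5.2 as written. No efficacy analysis uses this variable.

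Two stronger conclusions are tempting and are not supported:

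- A reader might infer that the protocol's own safety endpoint is emptied. It is not. That endpoint counts reported hypoglycaemia, and the meter rule admits AE-linked values. Only CGM discretion could reduce it.
- A reader might take the SAP's 54 mg/dL lower bound for an error. It agrees with 5.3.5.6, under which a non-AE below 54 mg/dL should not exist. A CGM reading that falls through is a failure of AE reporting, to be caught there.

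**What to change.** Reconcile the sections, using the criteria already in 5.3.5.6 and changing no clinical threshold.

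1. In Protocol 5.3.5.2, make hypoglycaemic episodes that meet the 5.3.5.6 criteria an exception to the AE-linked restriction. Enter each in the eCRF with glucose value, date, time, symptom status and device, whether or not it is an AE. Cross-refer the two sections.
2. State in 5.3.5.2 that investigator discretion over CGM readings does not override the AE requirement in 5.3.5.6.
3. Record CGM data per episode and define an episode beforehand. The SAP counts same-day hypoglycaemia with different start times as separate events, so entering every reading would inflate counts for CGM users relative to meter users.
4. Keep the SAP's 54 mg/dL bound. Query any recorded non-AE value below 54 mg/dL against 5.3.5.6.

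For data already collected, the meter printouts that 5.3.5.2 places in the medical records may allow missing values to be retrieved. The cost is a few sentences in the protocol, a device field if the eCRF lacks one, a note to sites, slightly more data entry, and possibly a less favourable hypoglycaemia count.

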5.3.5.3 Self-blood ketone monitoring

Patients will be equipped with an electronic device to determine their ketone concentration (i.e. the electronic blood glucose monitoring device/meter that is also capable of measuring blood ketones). The patient or his/her parent(s)/legal guardian will be asked to enter data from the device to a patient diary. The investigator or delegated site personnel should also print out the record list and include it in the patient medical records.

Patients should be instructed to test their ketones in case of any symptoms of DKA, e.g. nausea, vomiting, abdominal pain etc., irrespective of the glucose value. Patients must be reminded about the signs and symptoms of DKA, on the interpretation of ketone values measured via the meter, and on appropriate action to take in the event of increased ketone levels (see below).

Daily measurements before breakfast are recommended during the first 4 weeks of the treatment period and during the 4 subsequent weeks after Visit 5. Otherwise, measurements should be performed at least 3 times per week. In addition, blood ketone levels will be checked by using the meter at most clinic visits (see [Flow Chart](#)).

Daily blood ketone monitoring should also be performed in case of concomitant illness/stress or if deemed necessary by the investigator. In the event of increased ketones (> 0.6 mmol/l), patients should contact their trial site. In case of deteriorating ketosis, blood glucose and ketone levels should be checked every 1-2 hours until they are back in a range considered to be normal for the patient. Patients should be instructed to immediately refer themselves to hospital and/or the investigator, or to contact an emergency physician, in case of a blood ketone concentration > 1.5 mmol/L (as indicated in the meter manual). Blood ketone concentration > 1.5 mmol/L should be reported as AE by the investigator and the blood ketone values should be recorded in the eCRF.

In case of a suspected DKA, the investigator should ensure that appropriate tests are performed at the earliest opportunity according to local guidelines, such as a blood gas test (pH, bicarbonate). The results will be collected on the relevant page of the eCRF.

Investigators should also differentiate deteriorating ketosis/DKA from any mild to moderate increase of ketones which may be seen due to the mechanism of action of empagliflozin, especially in the fasted state (e.g. in the morning). In accordance with [Section 3.3.2](#), investigators should carefully select patients for the study in terms of their ability to comply with ketone measurement requirements. Patients not adhering to the instructions given by the investigator should be retrained at the earliest possible opportunity.

5.3.5.4 C-peptide

Laboratory samples for C-peptide will be collected at the time points indicated in the [Flow Chart](#).

Except for the screening visit, samples will be collected from the patient after an overnight fast (i.e. nothing to eat or drink except water for at least 8 hours). When applicable, samples should be collected before trial medication is taken.

The analysis will be performed by a central laboratory. Non-fasting serum C-peptide at Visit 1A will be used to check the patient eligibility as described in [Section 3.3.1](#). The respective reference ranges and details about sample handling and shipment will be provided in the laboratory manual in the ISF.

5.3.5.5 Tanner staging (modified)

Tanner staging is a scale of pubertal development in children, adolescents and adults which is routinely used for defining physical measures of development based on external primary and secondary sex characteristics, such as the size of the breasts, genitalia and development of pubic hair. Due to natural variation, individuals pass through the Tanner stages at different rates depending on the timing of puberty.

To assess the stage of puberty of each patient throughout the trial, a modified version of this scale will be used at the time points indicated in the Flow Chart. For patients with Tanner stage V at Visit 2, further assessment is not required at the subsequent visits. For details regarding the modified Tanner staging, please refer to [Appendix 10.1](#).

5.3.5.6 Criteria for hypoglycaemic event

Every episode of plasma glucose equal to or below 70 mg/dl (3.9 mmol/l) should be documented in the eCRF with the respective time and date of occurrence. Any hypoglycaemia with glucose values < 54 mg/dl (< 3.0 mmol/l) as well as all symptomatic and severe hypoglycaemic event (requiring active assistance by another person to administer carbohydrate) should be documented with the respective time and date of occurrence as an AE "hypoglycaemic event".

For the analysis, all hypoglycaemias will be classified according to the following criteria:

- Documented symptomatic hypoglycaemia AE with glucose concentration \leq 70 mg/dL (< 3.9 mmol/L), as well as asymptomatic hypoglycaemia event \leq 70 mg/dL (< 3.9 mmol/L)
- Documented any hypoglycaemia AE with glucose concentration < 54 mg/dL (< 3.0 mmol/L)
- Severe hypoglycaemia AE: event requiring the assistance of another person to actively administer carbohydrates, glucagon or take other corrective actions. Plasma glucose concentrations may not be available during an event, but neurological recovery following the return of plasma glucose to normal is considered sufficient evidence that the event was induced by a low plasma glucose concentration [R17-0216].

5.3.6 Assessment of adverse events

5.3.6.1 Definitions of AEs

Adverse event

An adverse event (AE) is defined as any untoward medical occurrence in a patient or clinical investigation subject administered a medicinal product and which does not necessarily have to have a causal relationship with this treatment.

An AE can therefore be any unfavourable and unintended sign (including an abnormal laboratory finding), symptom, or disease temporally associated with the use of a medicinal product, whether or not considered related to the medicinal product.

Serious adverse event

A serious adverse event (SAE) is defined as any AE which fulfils at least one of the following criteria:

- results in death,
- is life-threatening, which refers to an event in which the patient was at risk of death at the time of the event; it does not refer to an event that hypothetically might have caused death if more severe.
- requires inpatient hospitalisation or
- requires prolongation of existing hospitalisation,
- results in persistent or significant disability or incapacity, or
- is a congenital anomaly / birth defect, or

- is deemed serious for any other reason if it is an important medical event when based on appropriate medical judgement which may jeopardise the patient and may require medical or surgical intervention to prevent one of the other outcomes listed in the above definitions.
Examples of such events are intensive treatment in an emergency room or at home for allergic bronchospasm, blood dyscrasias or convulsions that do not result in hospitalisation or development of dependency or abuse.

AEs considered “Always Serious”

Cancers of new histology and exacerbations of existing cancer must be classified as a serious event regardless of the time since discontinuation of the drug and must be reported as described in [Section 5.3.6.2](#), subsections “AE Collection” and “AE reporting to sponsor and timelines”.

In accordance with the European Medicines Agency initiative on Important Medical Events, Boehringer Ingelheim has set up a list of further AEs, which by their nature, can always be considered to be “serious” even though they may not have met the criteria of an SAE as defined above.

The latest list of “Always Serious AEs” can be found in the eDC system. These events should always be reported as SAEs as described above.

Adverse events of special interest (AESIs)

The term AESI relates to any specific AE that has been identified at the project level as being of particular concern for prospective safety monitoring and safety assessment within this trial, e.g. the potential for AEs based on knowledge from other compounds in the same class.

AESIs need to be reported to the sponsor’s Pharmacovigilance Department within the same timeframe that applies to SAEs.

Protocol-specified AESIs (as identified by the investigator based on the below list for adverse events of special interest) can be classified as serious or non-serious but all these AESIs once identified by the investigator must be reported on an SAE form in an expedited manner similar to SAEs, even if they do not meet any of the SAE seriousness criteria (i.e. non serious AESI should be reported as a non-serious event on the SAE form for reporting).

The following events are considered as protocol-specified adverse events of special interest (AESI):

- Hypersensitivity reactions such as angioedema, angioedema-like events, and anaphylaxis (an identified risk with DPP-4 inhibitors)
- Skin lesions such as exfoliative rash, skin necrosis, or bullous dermatitis (a potential risk with DPP-4 inhibitors)
- Pancreatitis (an identified risk with DPP-4 inhibitors)
- Pancreatic cancer (a potential risk with DPP-4 inhibitors)
- Hepatic injury (of potential interest for all investigational drugs)
- Decreased renal function (of potential interest for all investigational drugs)
- Diabetic Ketoacidosis (DKA) (an identified risk with SGLT-2 inhibitors)

- Events involving lower limb amputation (a potential risk with SGLT-2 inhibitors)

Details on hepatic injury, decreased renal function, DKA and events involving lower limb amputation are provided below.

Hepatic injury

A hepatic injury is defined by the following alterations of hepatic laboratory parameters after randomisation:

- an elevation of AST and/or ALT ≥ 3 fold ULN combined with an elevation of total bilirubin ≥ 2 fold ULN measured in the same blood draw sample, and/or
- isolated elevation of ALT and/or AST ≥ 5 fold ULN

These laboratory findings constitute a hepatic injury alert and the patients showing these laboratory abnormalities need to be followed up according to the “DILI checklist” provided in the eDC system.

In case of clinical symptoms of hepatic injury (icterus, unexplained encephalopathy, unexplained coagulopathy, right upper quadrant abdominal pain, etc.) without lab results (ALT, AST, total bilirubin) available, the investigator should make sure these parameters are analysed, if necessary in an unscheduled blood test. Should the results meet the criteria of hepatic injury alert, the procedures described in the “DILI checklist” should be followed.

Decreased renal function

Decreased renal function diagnosed as acute kidney injury or defined by a creatinine value showing a ≥ 2 fold increase from baseline and is above the ULN.

For the AESI “decreased renal function” the investigator shall collect an unscheduled laboratory sample for creatinine as soon as possible and initiate follow-up laboratory tests of creatinine according to medical judgement.

Diabetic ketoacidosis (DKA)

DKA is defined by the diagnostic criteria in [Table 5.3.6.1: 1](#) below, and as defined by the American Diabetes Association (ADA) [[R14-5435](#)].

Investigators should note that not all criteria in the table below need to apply for the diagnosis of DKA, and clinical judgement should also be taken into consideration. Due to its mechanism of action, empagliflozin may potentially modify the clinical presentation of DKA which may occur at lower plasma glucose levels than stated in [Table 5.3.6.1: 1](#) below (see [Sections 1.2.1](#) and [2.3](#) for further details).

Table 5.3.6.1: 1 Diagnosis criteria for DKA according to the American Diabetic Association

	DKA		
	Mild	Moderate	Severe
Plasma glucose (mg/dL)	>250 [§]	>250 [§]	>250 [§]
Arterial pH	7.25-7.30	7.00-7.24	<7.00
Serum bicarbonate (mEq/L)	15-18	10 to <15	<10
Urine ketones*	Positive	Positive	Positive
Serum ketones*	Positive	Positive	Positive
Effective serum osmolality (mOsm/kg)**	Variable	Variable	Variable
Anion gap***	>10	>12	>12
Alteration in sensoria or mental obtundation	Alert	Alert/drowsy	Stupor/coma

§ In patients treated with SGLT2-inhibitors, including empagliflozin, a plasma glucose < 250 mg/dl does not exclude the diagnosis of DKA. In these patients DKA may occur at lower plasma glucose levels

* Nitroprusside reaction method

** Calculation: $2[\text{measured Na (mEq/L)} + \text{glucose (mg/dL)}]/18$

*** Calculation: $(\text{Na}^+) - (\text{Cl}^- + \text{HCO}_3^-)$ (mEq/L)

Events involving lower limb amputation

This definition includes amputation (i.e. resection of a limb through a bone), disarticulation (i.e. resection of a limb through a joint) and auto-amputations (i.e. spontaneous separation of non-viable portion of the lower limb).

Not included in this definition are debridement (removal of callus or dead tissue), procedures on a stump (like stump revision, drainage of an abscess, wound revision etc.) and other procedures (e.g. nail resection or removal) without a concomitant resection of a limb (amputation or disarticulation).

Each lower limb amputation, disarticulation, or auto-amputation should be reported separately. The SAE report should include the date of the procedure, the level of amputation or disarticulation, the medical condition(s) leading to the procedure and if the patient had some of the known risk factor(s) for lower limb amputation.

In addition to the safety topics defined as AESI above, the following safety topics will be monitored during the trial and assessed: Arthralgia, bullous pemphigoid, genital infections (including mycotic infections, such as vulvovaginal or balanitis), bone fracture, urinary tract infections (including urosepsis or pyelonephritis), AEs related to reduced intravascular volume and osmotic diuresis (including symptomatic hypotension).

Intensity of AEs

The intensity of the AE should be judged based on the following:

Mild:	Awareness of sign(s) or symptom(s) that is/are easily tolerated
Moderate:	Sufficient discomfort to cause interference with usual activity
Severe:	Incapacitating or causing inability to work or to perform usual activities

Causal relationship of AEs

Medical judgement should be used to determine the relationship, considering all relevant factors, including pattern of reaction, temporal relationship, de-challenge or re-challenge, confounding factors such as concomitant medication, concomitant diseases and relevant history.

Arguments that may suggest that there is a reasonable possibility of a causal relationship could be:

- The event is consistent with the known pharmacology of the drug.
- The event is known to be caused by or attributed to the drug class.
- A plausible time to onset of the event relative to the time of drug exposure.
- Evidence that the event is reproducible when the drug is re-introduced.
- No medically sound alternative aetiologies that could explain the event (e.g. pre-existing or concomitant diseases, or co-medications).
- The event is typically drug-related and infrequent in the general population not exposed to drugs (e.g. Stevens-Johnson syndrome).
- An indication of dose-response (i.e. greater effect size if the dose is increased, smaller effect size if dose is diminished).

Arguments that may suggest that there is no reasonable possibility of a causal relationship could be:

- No plausible time to onset of the event relative to the time of drug exposure is evident (e.g. pre-treatment cases, diagnosis of cancer or chronic disease within days / weeks of drug administration; an allergic reaction weeks after discontinuation of the drug concerned).
- Continuation of the event despite the withdrawal of the medication, taking into account the pharmacological properties of the compound (e.g. after 5 half-lives). Of note, this criterion may not be applicable to events whose time course is prolonged despite removing the original trigger.
- Additional arguments amongst those stated before, like alternative explanation (e.g. situations where other drugs or underlying diseases appear to provide a more likely explanation for the observed event than the drug concerned).
- Disappearance of the event even though the trial drug treatment continues or remains unchanged.

